12.7 Exploratory analysis

Cohen's kappa and its 95% confidence interval will be calculated for PD-L1 expression between primary tumor tissue and metastatic post first-line chemotherapy tumor tissue in n=14 subjects. This sample size will lead to a power of 0.80 to detect a kappa \geq 0.70 against the null hypothesis kappa=0. Otherwise, the statistical analysis for correlative endpoints will be descriptive and

hypothesis generating in nature. Descriptive statistics, statistical plot, correlations and appropriate statistical modeling will be used.

12.8 Safety stopping rule

The Data and Safety Monitoring Board will examine the overall safety data regularly and decide whether the trial should continue as detailed in Section 13 based on the totality of the data. In addition, a stopping rule will be employed after 25 and 50 subjects finish at least one cycle of treatment in the Experimental Arm B, respectively. This safety stopping rule will be performed with respect to two criteria: definitely treatment-related deaths and grade 4 treatment-related AEs. Two-sided 90% exact binomial confidence intervals (CIs) will be constructed. If their lower bounds exceed pre-defined levels, the study drug will be considered unacceptably toxic for this patient population and the study will be terminated.

The package insert of another monoclonal antibody to PD1 indicates a fatal pneumonitis rate of 0.3-0.9%⁴⁴. In addition, there have been other rare fatal events described with PD1 blockade. Consequently, if the lower bounds of the CIs of definitely treatment-related death rate exceed 0.9%, the study will be terminated. This corresponds to $\geq 2+$ (2 or more) out of 25 and $\geq 3+$ out of 50 subjects in the Experimental Arm B.

Previous studies reported a rate of 12% for grade 3-4 AEs.²⁷ Since the expected median PFSs are small for this patient population, we choose to focus on treatment-related grade 4 AEs. A rate of 10% is chosen that if the lower bounds of the CIs exceed 10%, enrollment will be halted and the study will be reviewed for continuation by the Data and Safety Monitoring Board. This corresponds to 6+ out of 25 and 10+ out of 50 subjects in the Experimental Arm B.

There will be no planned interim efficacy assessment.

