12 STATISTICAL CONSIDERATION

12.1 Study design

This is a multi-institutional, randomized, placebo controlled, double-blinded phase II trial. Eligible subjects will be 1:1 randomized to placebo (Control Arm A) and pembrolizumab (Experimental Arm B). Stratification factors for randomization include: presence of visceral metastatic disease (lung, liver, or bone vs. none) at the time of initiation of first-line chemotherapy, and response to first-line chemotherapy (CR/PR vs. SD).

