13.2 Data Safety Monitoring Board

The Data Safety Monitoring Committee (DSMC) at Tisch Cancer Institute (TCI) at the Icahn School of Medicine at, Mount Sinai Medical Center (MSMC) will serve as the primary Data and Safety Monitoring Board (DSMB) for this trial. They will review and monitor study progress, toxicity, safety and other data from this trial. Questions about subject safety or protocol performance will be addressed with the sponsor-investigator, statistician and study team members. Should any major concerns arise; the DSMB will offer recommendations regarding whether or not to suspend the trial.

The DSMB will meet quarterly and information provided may include: subject accrual, treatment regimen information, adverse events and serious adverse events reported by category, summary of any deaths on study, audit and/or monitoring results.

The DSMB will provide a recommendation to the team after all information is reviewed. This information should also be provided to the IRB at the time of continuing review for the trial.

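### The toxicity limits in section 12.8 are read only at 25 and 50 Arm B subjects, so no written action follows when a cumulative limit is reached before the look it decides

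*Combined protocol and SAP*

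**What the plan says.** Section 12.8 first gives the DSMB a regular review of overall safety on the totality of the data. It then adds a numerical rule: "a stopping rule will be employed after 25 and 50 subjects finish at least one cycle of treatment in the Experimental Arm B, respectively". The method is stated: "Two-sided 90% exact binomial confidence intervals (CIs) will be constructed".

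There are two criteria:
- **Definitely treatment-related deaths:** "if the lower bounds of the CIs of definitely treatment-related death rate exceed 0.9%, the study will be terminated". The stated limits are 2 or more of 25 and 3 or more of 50.
- **Treatment-related grade 4 AEs:** "if the lower bounds of the CIs exceed 10%, enrollment will be halted", with review by the DSMB. On the limits: "This corresponds to 6+ out of 25 and 10+ out of 50 subjects in the Experimental Arm B".

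Section 13.2 describes the standing review: "The DSMB will meet quarterly and information provided may include: subject accrual, treatment regimen information, adverse events and serious adverse events reported by category". The DSMB may recommend suspending the trial, and no count or rate is attached to that. Section 11.2.2.1 has sites report SAEs to HCRN within 24 hours. No section says what happens if one of the 12.8 counts is reached before its look.

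**The concern.** A cumulative count cannot fall, unless an attribution is revised. If 2 of the first 10 Arm B subjects have a definitely related death, the count at 25 will be at least 2 whatever happens to the next 15. The 25-subject look is then already decided, and section 12.8 says the study is terminated. Read literally, the rule still waits for those 15 subjects to be randomized and finish a cycle. The same gap recurs between the two looks.

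The wait adds no information to the decision. It matters only when the drug is more toxic than the levels in 12.8 allow, which is the case the rule was written for. What is at stake is exposure of further subjects in Arm B, plus placebo subjects entering a trial whose own rule has already been met.

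**Working it through.** **Inputs from the documents.** Looks at 25 and 50 Arm B subjects, two-sided 90% exact intervals, levels of 0.9% and 10% (12.8); 108 subjects and 24 to 36 months of enrollment (synopsis); 1:1 allocation (12.1); three-week cycles (5.1).

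**Assumptions.** True event rates other than 0.9% and 10%; uniform accrual; exact balance at each look; events known at once, except where delayed onset is stated.

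**1. The plan's limits reproduce.** The exact lower bound for x of n is the 5% quantile of Beta(x, n − x + 1).

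| Criterion | Limit | Lower bound | One fewer |
|---|---|---|---|
| Death, 0.9% | 2/25 | 1.44% | 1/25: 0.20% |
| Death, 0.9% | 3/50 | 1.66% | 2/50: 0.72% |
| Grade 4, 10% | 6/25 | 11.0% | 5/25: 8.2% |
| Grade 4, 10% | 10/50 | 11.3% | 9/50: 9.7% |

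**2. When the looks fall.** Accrual is 108/24 = 4.5 to 108/36 = 3 subjects a month. Look 1 needs about 50 randomized plus 2 to 3 more during one cycle: 52 to 53 of 108 (48% to 49%), at about month 12 to 17. Look 2 falls at about 102 to 103 of 108 (95%).

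**3. Stopping probability, events known at once.** An exact subject-by-subject recursion compared the two-look rule with the same counts acted on when reached (the 25-subject limit up to subject 25, then the 50-subject limit). The probabilities are identical:
- Deaths: 2.6% at a true rate of 0.9%, 52% at 5%, 81% at 8%.
- Grade 4: 4.7% at 10%, 61% at 20%, 97% at 30%.

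**4. How early the first-look limit is reached.** Let P be the probability that look 1 stops and m the mean Arm B subject number at which the limit is reached, given that it stops. The conditional saving is 25 − m; the unconditional saving is P × (25 − m).

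| Criterion, true rate | P | m | 25 − m | P × (25 − m) |
|---|---|---|---|---|
| Death 0.9% | 0.021 | 17.0 | 8.0 | 0.17 |
| Death 5% | 0.358 | 15.5 | 9.5 | 3.4 |
| Death 8% | 0.605 | 14.3 | 10.7 | 6.5 |
| Grade 4 20% | 0.383 | 19.8 | 5.2 | 2.0 |
| Grade 4 30% | 0.807 | 17.4 | 7.6 | 6.1 |

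For deaths at 5% to 8%, the conditional saving is 2 × 9.5 = 19 to 2 × 10.7 = 21 subjects over both arms. That is 19/4.5 = 4.2 to 21/3 = 7 months of accrual. About half of these subjects would receive placebo.

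**5. Delayed onset.** Take an assumed exponential onset with mean 4 months and 2.25 Arm B entries a month. The conditional grade 4 saving at 20% to 30% is then about 4 to 5 Arm B subjects. With immediate onset on the same calendar it is about 7 to 9: the 5.2 to 7.6 above plus roughly 1.6 entering during the three-week cycle.

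**6. The wording of a fix matters.** If the 25-subject limit stayed in force for the first 25 subjects after look 1, late events would go on counting against it. With the same delayed onset, the chance of stopping at a true 10% grade 4 rate would rise from about 1.2% to between 3.3% (counted to look 2) and 4.7% (no time limit). If each limit applies only until its own look, any early crossing is also a crossing at that look, so the probability does not move whatever the onset pattern.

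**The case against.** The strongest reply is that the numerical rule is not the trial's only safety control. Section 12.8 puts regular DSMB review first and the limits second. The DSMB meets quarterly, SAEs reach HCRN within 24 hours and the sponsor-investigator within one further business day (11.3), and expedited FDA reporting applies (11.4). A reader might infer that a limit reached early triggers nothing, or that half the trial runs without safety control. The documents do not support that: the DSMB can act on its own judgement at any meeting, so the fair comparator for a delay of 4 to 7 months is a meeting within about three months. What remains is that this review has no threshold, that 12.8 adds the limits on top of it, and that 3 × 3 = 9 to 3 × 4.5 = 13.5 subjects may be randomized between meetings.

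The size is also open to challenge. The conditional savings rest on assumed definite-death rates of 5% to 8%, far above the 0.3% to 0.9% fatal pneumonitis rate that 12.8 cites. Section 5.1.3.4 says events may appear months after the last dose, which shortens the grade 4 lead. Both objections stand, and the unconditional and delayed-onset figures reflect them.

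A reader might also infer that any form of continuous monitoring is free. It is not. Step 6 shows one form that raises the chance of stopping. Recomputing the interval after every subject would be another rule again: one death in the first 5 gives a lower bound of at least 1.02%, and at a true 0.9% that has probability 1 − 0.991^5 = 4.4%.

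**Conclusion.** The point holds for the numerical rule and for nothing wider. The four limits are computed correctly, and an early crossing is delayed, not lost. The defect is that a look whose result is already fixed has to wait for its denominator. If the first look is going to stop, the wait averages about 9 to 11 Arm B subjects for deaths at assumed rates of 5% to 8%. For grade 4 events at 20% to 30% it is about 5 to 8, or about 4 to 5 on the delayed-onset calendar. At the benchmark death rate of 0.9% the expected first-look saving is negligible (0.17 Arm B subjects).

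This is an inexpensive improvement to a sound rule, not an error in it. It rests on uniform accrual, on the assumed true rates, and on counting the same Arm B subjects before the look as at it.

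**What to change.** Keep the sponsor's limits, levels and two looks. Add to 12.8 that if the count for the upcoming look is reached before that look, the look is carried out at once and referred to the DSMB. The 25-subject limit applies until look 1 is done, and the 50-subject limit from then until look 2. State that the 25-subject limit is not applied after look 1, and that the running count uses the same Arm B subjects that the look will count. For this, 12.8 must say whether a subject who dies or stops before finishing cycle 1 is included. With this wording the probability of stopping is unchanged and only the timing moves.

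The cost is a running tally by HCRN staff who are already unblinded (12.9), and a possible unscheduled DSMB review. Related grade 4 AEs must also be flagged promptly with their attribution, because a grade 4 AE is not automatically an SAE under 11.1.2 and the 24-hour stream will not capture all of them.

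Separately, 12.8 gives two consequences for the grade 4 criterion: its general sentence terminates the study, while the grade 4 sentence halts enrollment pending DSMB review. The sponsor must reconcile these. No new threshold or clinical rule is proposed here.

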11.2.2.2 HCRN Requirements for Reporting SAEs to Merck

Hoosier Cancer Research Network will report any possibly related and unexpected SAE to Merck **within one business day** of receipt of the SAE/ECI Submission Form and to regulatory authorities (FDA) per federal guidelines. Follow-up information will be provided to Merck as it is received from site.

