12.3 Definitions of secondary endpoints

- PFS, which is defined as the time from randomization to death or progression, depending on which occurs first as defined by RECIST 1.1.
- PFS as per irRECIST and RECIST 1.1 by PD-L1 expression levels.
- Six-month PFS rate, which is defined as the percentage of participants that are alive and progression-free, as per irRECIST and RECIST 1.1, at six months calculated from the date of randomization.
- Six-month PFS rate as per irRECIST and RECIST 1.1 by PD-L1 expression levels.
- Safety of pembrolizumab, defined as rates of Grade 1-5 toxicity according to CTCAE v4.0.
- Objective response rate (ORR) in subjects on maintenance pembrolizumab versus placebo, which is defined by irRECIST and RECIST 1.1 in subjects with measurable disease.
- ORR in subjects receiving pembrolizumab after progressing on placebo as per irRECIST and RECIST 1.1.
- Overall survival (OS), which is defined as the time from randomization to death.

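### A fatal event rated possibly or probably related counts toward neither numerical limit in the 12.8 stopping rule, although the same event at grade 4 would count

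*Combined protocol and SAP*

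**What the plan says.** Section 12.8 adds a formal rule to the DSMB's regular safety review. It is applied twice: "a stopping rule will be employed after 25 and 50 subjects finish at least one cycle of treatment in the Experimental Arm B". It names two criteria for what is counted: "definitely treatment-related deaths and grade 4 treatment-related AEs". On the method: "Two-sided 90% exact binomial confidence intervals (CIs) will be constructed".

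- **Deaths.** "if the lower bounds of the CIs of definitely treatment-related death rate exceed 0.9%, the study will be terminated". The stated limits are 2 or more of 25 and 3 or more of 50. The 0.9% is the top of a range for fatal pneumonitis in the package insert of another PD-1 antibody.
- **Grade 4 events.** A lower bound above 10% halts enrollment for DSMB review. The stated limits are 6 or more of 25 and 10 or more of 50. There is no attribution requirement beyond treatment-related.

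Section 11.1.6 gives five levels of relatedness: unrelated, unlikely, possible, probable, definite. Section 12.3 lists as a secondary endpoint: "Safety of pembrolizumab, defined as rates of Grade 1-5 toxicity according to CTCAE v4.0". Section 11.2.2.2 uses a lower attribution bar for expedited reporting: "Hoosier Cancer Research Network will report any possibly related and unexpected SAE to Merck".

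**The concern.** The two criteria do not meet. The first takes deaths, but only at the top level of relatedness. The second takes any treatment-related event, but only at grade 4. A death rated possible or probable is too weakly attributed for the first and too severe for the second.

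The result runs against the order of severity: a probably related pneumonitis counts if it is recorded at grade 4, and does not count if it is recorded only as fatal. At stake is whether the one objective trigger in the safety plan responds to fatal toxicity whose attribution is likely but not certain.

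**Working it through.** **1. The plan's own limits.** The exact two-sided 90% lower bound for x events in n subjects is the 5% quantile of a Beta(x, n − x + 1) distribution. The limit is the smallest x whose bound exceeds the stated level.

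| Criterion | Level | n | Bound one below the limit | Bound at the limit | Stated limit |
|---|---|---|---|---|---|
| Definite deaths | 0.9% | 25 | 1/25: 0.21% | 2/25: 1.44% | 2+ |
| Definite deaths | 0.9% | 50 | 2/50: 0.72% | 3/50: 1.66% | 3+ |
| Grade 4 related | 10% | 25 | 5/25: 8.23% | 6/25: 11.01% | 6+ |
| Grade 4 related | 10% | 50 | 9/50: 9.72% | 10/50: 11.27% | 10+ |

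All four limits reproduce. The point concerns which events enter the counts, not the arithmetic.

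**2. Which events count.** Grade 5 is read as death, the usual CTCAE meaning; 12.3 itself shows only that grade 5 is distinct from grade 4.

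| Event in Arm B | Death count | Grade 4 count |
|---|---|---|
| Grade 4, treatment-related | no | yes |
| Fatal, definite | yes | no |
| Fatal, probable | no | no |
| Fatal, possible | no | no |

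**3. Example.** Five of 25 subjects have probably related deaths, with no grade 4 record and no definite death. The counts are 0 and 0, and no limit is crossed. The lower bound for 5/25 is 8.2%, about nine times the 0.9% level (8.2 / 0.9 = 9.1).

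**4. Two-look probabilities.** With the first 25 subjects nested in the 50, limits r1 and r2, and a rate p of counted events:

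P(cross by 50) = P(X ≥ r1) + Σ over x < r1 of P(X = x) · P(Y ≥ r2 − x), where X and Y are independent Binomial(25, p).

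*Adding grade 5 to the second criterion (6/25, 10/50).* The event rates are assumptions.
- Grade 4 alone at 10%: 0.033 at 25, 0.047 by 50.
- 10% grade 4 plus a further 5% of subjects with related grade 5, so p = 15%: 0.162 at 25, 0.265 by 50.
- Related deaths alone at 8%, with no grade 4 events: 0.012 at 25, 0.016 by 50.

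*The death criterion (2/25, 3/50).*
- Counted deaths at 0.9%: 0.021 at 25, 0.026 by 50.
- Counted deaths at 3%: 0.17 at 25, 0.25 by 50.
- Related deaths at an assumed 8%, by the share rated definite: all, 0.61 and 0.81; half (p = 4%), 0.26 and 0.39; a quarter (p = 2%), 0.09 and 0.12. The documents give no such share, so 25% to 100% is only a range for illustration.

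**The case against.** The strongest reply is that these deaths are not unmonitored. Section 12.8 opens with the DSMB deciding on continuation from all the safety data, and the counts come on top of that. Section 13.2 has the DSMB meet quarterly, with deaths on study among the material it may receive. SAEs reach the coordinating network within 24 hours (11.2.2.1), and the sponsor-investigator then assesses relatedness (11.3). All of this stands. What is missing is a numerical limit, not oversight.

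A second reply is that a strict attribution standard suits a limit that terminates the study at 2 of 25, in a population where deaths from disease are expected. That is defensible, although 12.8 does not give it as a reason. It argues against simply widening the death criterion. It does not explain why fatal events are left out of the second criterion, whose consequence is a halt for review.

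A reader might also infer three stronger things that the documents do not support:
- *That the rule misses most treatment-related deaths because few would be rated definite.* No section gives that share. The blinding argument is also weak: 7.3.2 and 12.9 provide for unblinding when treatment stops for unacceptable toxicity, and 7.3.2 allows it when a medical event requires it.
- *That an event already counted at grade 4 drops out if the subject later dies.* Section 12.8 does not say so, and an earlier grade 4 record in the same subject may still count.
- *That adding grade 5 to the second criterion gives a strong guard against deaths.* At an assumed 8% death rate with no grade 4 events, it is crossed by 50 with probability 0.016.

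**Conclusion.** The point holds as a gap in the numerical rule. On the scales in 11.1.6 and 12.3, a fatal event rated possible or probable enters neither count in 12.8, and the same event at grade 4 would. This rests on the wording, and on grade 5 meaning death; it needs no assumption about event rates.

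The practical size cannot be fixed from the documents, because neither the related-death rate nor the share rated definite is given. The probabilities above are illustrations under stated assumptions, and they leave out any action by the DSMB on its own judgement.

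Whether the 0.9% criterion should also take in probable deaths is a separate question and a real trade-off. In favour: the benchmark is a fatal pneumonitis rate that 12.8 does not tie to definite attribution, so count and benchmark may not match. Against: crossing that limit ends the study, with probability 0.25 by 50 if counted deaths run at 3%.

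**What to change.** In 12.8, change the second criterion to subjects with at least one grade 4 or 5 treatment-related AE. Keep the 10% level and the limits of 6/25 and 10/50. Grade and relatedness are already recorded, so the change is one phrase.

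The cost is a higher chance of an enrollment halt for DSMB review: 0.27 instead of 0.05 by the second look in the 10% plus 5% example. That assumes the halt-and-review sentence governs this criterion. An earlier sentence in 12.8 says that crossing the pre-defined levels terminates the study, and the two should be reconciled in the same edit.

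The sponsor and DSMB should separately decide, and record with a reason, whether probable deaths count toward the 0.9% criterion. If they do, the limits stay at 2/25 and 3/50 and only the counted events change. The price is a wider trigger for termination, and possibly related deaths would still count only under the amended second criterion.

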12.9 Unblinding plan

For purposes of protocol therapy distribution, all administrators of the EDC system at HCRN and participating site pharmacy personnel will be unblinded to the protocol therapy assignment. For the purpose of the interim analyses and the final analysis, the statistician and HCRN analysis staff will be unblinded.

Unblinding of the protocol therapy will occur at the time of disease progression or discontinuation of protocol therapy due to unacceptable toxicity (see Section 6), which are considered as medical emergencies. Please see Section 7.3.2 for additional information on unblinding.

Subjects randomized to treatment with placebo will be eligible to cross over for treatment with pembrolizumab provided that eligibility outlined in Section 3 is still met.

12.10 Analysis datasets

- Enrolled set. This will comprise all subjects who meet the eligibility criteria and are registered onto the study.
- Evaluable set. This will comprise all enrolled subjects who undergo at least one post-baseline assessment or die before any evaluation.

- Safety set. This will comprise all subjects that receive at least one dose of study drug.

12.11 Sample size calculation/Accrual/Study duration/Replacement rules

As described in section 12.5.

12.12 Subject characteristics and significant protocol violations

Demographic and other baseline data will be summarized descriptively for all subjects in the enrolled set. Significant protocol violations will be documented.

12.13 Concomitant medication

Concomitant medications and significant non-drug therapies prior and after the start of the study drug will be summarized for the safety set.

12.14 Disposition

The number of enrolled subjects will be summarized in a flow chart with frequency of completion and discontinuation. The subjects discontinued from study drug and their corresponding information will be listed. Significant protocol violations will be tabulated and/or listed.

